13. ALTERNATIVES TO STUDY PARTICIPATION

As stated in the current consent form, the alternative to study participation is to withdraw from the study.

14. POTENTIAL RISKS

Potential risks are minimal. The rating scales and questionnaires are innocuous. Startle testing exposes subjects to the application of skin tape electrodes and to brief loud sounds, which in >30 years of testing in the [name] and [name] laboratories has caused no side effects. All other measures require only computer keyboard use and involve no risk. The cumulative risks of this proposal are judged as small. Below is a summary of the language in the consents.

- 1. An alcohol swab is used to clean the skin before electrodes are applied and some minor skin irritation and redness may occur.
- 2. Some participants might experience fatigue, boredom or irritation during the test session.
- 3. Some participants may be embarrassed or feel uncomfortable by some of the questions asked in the questionnaires.
- 4. Eyeblink startle exposes subjects to the application of skin tape electrodes and to brief loud sounds, which in our experience has caused no side effects.
- 5. During the study, your blood pressure and pulse will be regularly monitored.
- 6. Blood drawing may cause a small amount of pain. In addition, a temporary bruise or "black and blue mark" may develop. Rarely, people faint after having their blood drawn. Very rarely, the vein in which the needle has been inserted may become inflamed or infected, which can be treated.

For the drug evaluation study, the proposed drugs carry a very small risk of toxicity or adverse side effects in the doses to be used in this study. The most common side effects associated with each drug are listed in Section 8 above, and typically include nausea, somnolence and dizziness. We do not plan to administer these drugs to subjects in whom it is contraindicated, such as subjects with known cardiovascular or neurological disorders. The doses selected for use in these studies are in the low- or below-therapeutic range for these drugs when they are used clinically, and in most cases, the selected dose is equal to or less than the lowest recommended starting clinical dose for the drug. To address the potential for some of these drugs to produce changes in blood pressure, we will carefully monitor subjects' vital signs, and will not release subjects from the hospital until their vital signs are within normal limits. To address the possible side effect of somnolence, we will instruct subjects to arrange for their transportation from the hospital on test days. For studies that include women of childbearing potential, there is the possibility of unforeseen harm to an unborn child due to the administration of drugs. To address this risk, all female subjects will be asked to provide a urine sample to test for pregnancy and we will exclude participants who test positive. Additionally, all female subjects in these studies will be required to use a non-drug birth control method, such as abstinence, diaphragm, non-hormone intrauterine device to prevent pregnancy during the study. Subjects will be told to report if their menstrual cycle is inconsistent or if suspect that they are pregnant. Drugs will be dispensed by a licensed physician, and a licensed physician will be present on the premises at all times during testing. The consent forms include the related risks specific to the drug it refers to.

15. RISK MANAGEMENT PROCEDURES AND ADEQUACY OF RESOURCES

The overall risks of this proposal are small. Protection of subject confidentiality and privacy will be rigorously guarded by the assignment of coded numbers to each file in the computer analysis and database. Resulting data will not be released to any subject, and released only to a patient's primary physician when an appropriate release form is signed by the patient. The UCSD psychophysiology research laboratory of [name] has studied over 1000 control subjects and patients without any problems with confidentiality.

For the drug evaluation study, risk management procedures include: 1) Subjects will be asked to refrain from alcohol or other drug use while on the study. 2) Each subject will receive a complete history and physical examination prior to acceptance into the study. 3) A battery of psychological tests will be administered, as will an EKG and urine toxicology screen (which will also be used to test for pregnancy in drug studies including women of childbearing potential). 4) Subjects involved in studies with drugs will arrange for their transportation from the hospital, and any subject reporting any sedation upon completion of the study will be instructed to not operate a motor vehicle until the sedation is resolved. Subjects known or determined to have cardiovascular disease by EKG or patient history will be excluded. All subject information will be kept in a secure and locked area of the laboratory, CTF Building, UCSD Medical Center. Confidentiality will be protected to the extent provided by law.

If a participant has any questions regarding the study, they may contact the PI, [name]., Ph.D., Monday-Friday, 8 a.m. – 4:30 p.m. at [contact]. He may be reached after hours by contacting the UCSD operator at [contact] and having them page [name]. If any emergencies arise related to participating in these studies, the participant may proceed to the nearest emergency room or call 9-1-1.

Subjects will be told that they can terminate the experiment at any time if an aspect of the procedure causes them discomfort.

Risks associated with specific study populations: Because the proposed studies include schizophrenia patients, it is important to consider any risks that might be specifically elevated in this study population. As noted above, clinical trials with schizophrenia patients in which daily dosing of 10 - 20 mg memantine was added to ongoing medications have generally reported no or minimal evidence of either clinical improvement or adverse events. Thus, the likelihood that a single pill of 10 - 20 mg memantine would be associated with clinical changes is low. The population of schizophrenia patients to be enrolled in these studies will come primarily or exclusively from subjects who are seeking enrollment in an existing protocol

for supported employment (#071306, [name], PI); based on this, they will most likely be high functioning, clinically stable, and (by definition) seeking employment. Nonetheless, should the subjects voice any thoughts of self-harm or suicidality, all testing staff are instructed to immediately contact the licensed physician who is on-site and covering each test session. The physician will then immediately evaluate the subject, and based on their clinical condition, might escort them across the street to the Emergency Room at the UCSD Medical Center for further evaluation and, if necessary, treatment. It is important to note that, in over 30 years of testing schizophrenia patients at the CTF in the laboratories of Drs. [name] and [name], including several thousand schizophrenia patients and several drug challenge studies, only 1 subject has ever required an escort to the UCSDMC Emergency Room.

16. PRIVACY AND CONFIDENTIALITY CONSIDERATIONS INCLUDING DATA ACCESS AND MANAGEMENT

All data and specimens are de-identified, and coded numbers are assigned to each file in the computer analysis and database. Research records are kept in a room separate from the data and specimens. Both the separate room and the filing cabinet containing the records are locked. Only the study coordinator has the key to access the files. Subject unique identifiers (name, DOB, SS#, etc.) will never be connected with the de-identified data. When published, data will remain de-identified, though subjects' non-unique demographic information (age, sex, ethnicity, handedness, diagnosis) may be reported together with the de-identified data. No other information will be provided to entities beyond the PI and key personnel noted in this application. The PI's UCSD research laboratory has studied over 1000 subjects and patients without any problems with confidentiality.

Positive drug screen results, if they became known outside the research, could reasonably place the subject at risk of criminal civil liability or be damaging to the subject's financial standing or employability. There is also the possibility of loss of confidentiality. Research records will be kept confidential to the extent allowed by the law. A study number will be used to identify information from participants. The database that relates the participants to a specific study number will be maintained using initials. Any database file will be encrypted on a password-protected computer.

All recruitment, interviewing, consenting, physical examinations and testing will take place in a private setting, specifically a dedicated interview room at the UCSD Medical Center, occupied only by the interviewing staff, physician and test subject, with the door closed, and a "DO NOT DISTURB" sign posted on the door.

It is NOT reasonably foreseeable that the study will collect information that Federal, State, and/or local laws/regulations requires to be reported to other officials (e.g., child or elder abuse; positive results from lab tests). However, as is true of any clinical population, and particularly in patients with brain disorders, it is possible that subjects may exhibit severe psychiatric symptoms including the description of suicidal ideation. An on-call licensed physician is covering all studies; should any such clinical issues arise, the covering physician will be contacted and will assess the situation for the most appropriate clinical intervention.

17. POTENTIAL BENEFITS

The information gained in these studies is expected to lead directly to a greater understanding of the pathophysiology of serious illnesses, and will facilitate the development of novel treatment strategies. For the drug evaluation study, those likely to benefit most from the proposed project are severely ill psychiatric patients, as enhanced understanding of their cognitive and neurochemical abnormalities will allow for more accurate assessment and treatment of their symptoms. Individual subjects will benefit from a medical and psychological evaluation. Control subjects are unlikely to receive any other direct benefits from the proposed study other than the opportunity to contribute to efforts designed to relieve human suffering; there is evidence that participation in generative activities that improve self-esteem can have a positive impact on an individual's quality of life. Individuals with schizophrenia may or may not benefit from the long term goal of their study: to identify medications that will enhance the clinical impact of cognitive interventions in psychiatric patients.

18. RISK/BENEFIT RATIO

For the drug evaluation study, the risks from study participation include mild discomfort from drug effects, and the benefits include careful medical evaluation and potential gains in self-esteem among study participants, and significant benefit to patients in terms of knowledge gained related to the nature and optimal treatments of psychiatric disorders. The risk-benefit ratio of this study is very low.

19. EXPENSE TO PARTICIPANT

N/A

20. COMPENSATION FOR PARTICIPATION

The subjects will be paid \$30 for the SCREENING SESSION and \$130 for completion of the TEST SESSION. These payments have been accepted by the Human Subjects Committee as reasonable amounts for the length of subject participation. Subjects that participate in the "WITHIN-SUBJECT" study will be paid \$30 for the SCREENING SESSION, \$100 after the first test day and \$130 for the completion of the second test day. This is a total of \$260. Subjects will be reimbursed for parking costs on the SCREENING and TEST days and given breakfast and lunch on the TEST day.

Participants in the ONE-DAY study will be paid a total of \$30. Compensation will be prorated to \$10 per hour if the following happens: participants do not pass the tests; participants voluntarily withdraw from the study; or study personnel withdraw participants from the study.

23. FUNDING SUPPORT FOR THIS STUDY

The following are UCSD grants. [name] is the Fiscal Contact:

- NIDA 5R03 DA027483-02 (PI) 9/1/09 8/31/11
- NIMH R01 MH059803 (PI) 12/7/2010 11/30/2013

24. BIOLOGICAL MATERIALS TRANSFER AGREEMENT

NA

25. INVESTIGATIONAL DRUG FACT SHEET AND IND/IDE HOLDER

NA

26. IMPACT ON STAFF

NA

27. CONFLICT OF INTEREST

NA

28. SUPPLEMENTAL INSTRUCTIONS FOR CANCER-RELATED STUDIES

NA

29. OTHER APPROVALS/REGULATED MATERIALS

NA

30. PROCEDURES FOR SURROGATE CONSENT AND/OR DECISIONAL CAPACITY ASSESSMENT

Schizphrenia patients who have been identified for participation in our studies will also be enrolled in IRBapproved clinical trials of cognitive training with [name]. [name] has approval to screen and administer surrogate identification process. Any patients that have been identified as having impairment in their decision-making ability will be determined by [name] and will not be referred to our studies.

Revision date: October 29, 2010

Statistical Analysis Plan Memantine Effects on Sensorimotor Gating and Neurocognition in Schizophrenia NCT03860597 R01MH094320 Latest IRB approval date: June 21, 2022 IRB expiration date: July 7, 2023

The primary statistical considerations for these data are those required to test the primary hypothesis that memantine (MEM) would enhance sensorimotor gating and related measures of auditory information processing in schizophrenia (SZ) patients. The operational measure of sensorimotor gating was prepulse inhibition of startle (PPI). The primary hypothesis was tested by a 2-way repeated-measure ANOVA of PPI with MEM dose and prepulse interval (10, 20, 30, 60 or 120 ms) as within subject factors. The key dependent measure was %PPI, calculated according to common practices in the literature. The hypothesis that MEM will increase PPI in SZ patients was to be confirmed by a significant main effect of drug (active > PBO) or significant interaction among the variables of drug, dose (10 or 20 mg), diagnosis (healthy subject (HS) or SZ) or prepulse interval, and informative post-hoc comparisons. The assumptions behind these analyses range from the standard assumptions underlying the use of parametric analyses, to those specific to prepulse inhibition, e.g. related to the potential confounding effects of drug or diagnosis effects on startle magnitude. Data were demonstrated to be normally distributed and drug effects on PPI were shown to be independent of changes in startle magnitude. Analyses confirmed the hypothesis for the 20 mg dose of MEM in SZ patients.

The operational measure of mismatch negativity (MMN) is mean amplitude in response to oddball stimuli over the 135-205 ms range. The primary hypothesis was tested by an ANOVA of MMN with MEM dose as a within subject factor. The hypothesis that MEM will increase MMN in SZ patients was to be confirmed by a significant main effect of drug (active > PBO) or significant interaction among the variables of drug, dose (10 or 20 mg), diagnosis (healthy subject (HS) or SZ), and informative post-hoc comparisons. The assumptions behind these analyses range from the standard assumptions underlying the use of parametric analyses. Data were demonstrated to be normally distributed. Analyses confirmed the hypothesis for the 20 mg dose of MEM in SZ patients.

The operational measure of the auditory steady-state response (ASSR) is 40-Hz evoked power. The primary hypothesis was tested by an ANOVA of ASSR with MEM dose as a within subject factor. The hypothesis that MEM will increase ASSR in SZ patients was to be confirmed by a significant main effect of drug (active > PBO) or significant interaction among the variables of drug, dose (10 or 20 mg), diagnosis (healthy subject (HS) or SZ), and informative post-hoc comparisons. The assumptions behind these analyses range from the standard assumptions underlying the use of parametric analyses. Data were demonstrated to be normally distributed. Analyses confirmed the hypothesis for the 20 mg dose of MEM in SZ patients.

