Main effects of memantine on WM will be tested by one-way ANOVA with memantine dose as a withinfactor. Based on d=0.73 for increased WM after 20 mg MEM in controls (see above), the proposed 30 patients/dose group would yield power of 0.79 to detect significant WM-enhancing effects. While preliminary data yield less robust predictions for COMT subgroup sensitivities in memantine effects on WM performance, given the significant correlation of WM and PPI, and known impact of COMT genotype on PPI levels, we predict some differential (Val/Val > Met/Met) memantine sensitivity in this measure. If we estimate effects of COMT status on WM memantine-sensitivity to be comparable to those for PPI (65% increase in effect size), then the estimated d for Val/Val vs. Met/Met sensitivity should be 1.20, and the proposed genotype subgroup sizes would yield power of 0.65 to detect genotype-sensitive memantine effects on WM.

Secondary "biomarkers" are MMN and GBS. For MMN, positive memantine effects will be detected by increased MMN amplitude at electrode Fz. For GBS, positive memantine effects would be detected by increased 40 Hz evoked power at electrode Fz. Unlike those for PPI, predictions of positive memantine effects on MMN and GBS are not based directly on previous findings from our laboratory, using measures identical to those proposed herein. However, based on reports in healthy subjects from other laboratories of memantine effects on MMN (d=0.87) and ketamine effects on GBS (d=0.69), the proposed 30 patients/dose group would yield power of 0.90 and 0.75, respectively, to detect positive memantine effects on these measures.

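### The SAP's confirmation rule for PPI, MMN and ASSR does not require an active > placebo effect within schizophrenia patients, and does not match the models the SAP names

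*SAP*

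**What the plan says.** The SAP's PPI paragraph names the primary test as a "2-way repeated-measure ANOVA of PPI with MEM dose and prepulse interval (10, 20, 30, 60 or 120 ms) as within subject factors". It then gives the decision rule. The first route reads "The hypothesis that MEM will increase PPI in SZ patients was to be confirmed by a significant main effect of drug (active > PBO"; no population is attached to that main effect. The second route is statistical significance of an "interaction among the variables of drug, dose (10 or 20 mg), diagnosis (healthy subject (HS) or SZ) or prepulse interval, and informative post-hoc comparisons".

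For MMN and ASSR the pattern is the same. The models are stated as "The primary hypothesis was tested by an ANOVA of MMN with MEM dose as a within subject factor" and "The primary hypothesis was tested by an ANOVA of ASSR with MEM dose as a within subject factor". The second route for each is a "significant interaction among the variables of drug, dose (10 or 20 mg), diagnosis (healthy subject (HS) or SZ), and informative post-hoc comparisons".

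Each of the three paragraphs ends with the same result: "Analyses confirmed the hypothesis for the 20 mg dose of MEM in SZ patients".

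The protocol is tighter. In section 9, part j, the PPI analysis in patients is confirmed by a dose effect (active > placebo), or by dose × interval with post-hoc comparisons at one or more intervals. Analyses are run separately for each dose group. For MMN the direction is given: "For MMN, positive memantine effects will be detected by increased MMN amplitude at electrode Fz". For gamma band synchronization (GBS, the SAP's ASSR) it is greater 40 Hz evoked power at the same electrode. Post-hoc comparisons use Tukey's tests and alpha is 0.05.

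**The concern.** A drug × diagnosis interaction shows that two groups respond differently. It does not show that patients respond. A drug main effect in a model containing both groups can likewise come from the healthy subjects alone. Both satisfy the SAP's wording, because the rule names no population for the main effect and does not say in which group, or in which direction, a post-hoc must be significant to count as informative.

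The rule also reaches beyond the model named for PPI, so some other, unstated model must supply the additional routes. At stake is whether a reader can tell which model and which contrast stand behind each of the three confirmed statements. The SAP gives no sample size, test statistic or p-value that would settle it.

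**Working it through.** **1. Rule against model.** The named PPI ANOVA has two within-subject factors, drug (placebo or active) and interval. It yields three terms: drug, interval, and drug × interval. Diagnosis is a between-subject factor. So is 10 versus 20 mg in patients, because under Aim 3 (protocol section 6) each patient takes placebo and one active dose. Of the interactions the rule admits, the named model can therefore test only drug × interval. A model with all four variables has 2⁴ − 1 − 4 = 11 interactions; 7 contain diagnosis, and 4 do not contain drug at all. For MMN and ASSR, three variables give 2³ − 1 − 3 = 4 interactions, 3 of them with diagnosis. The between-subject part of those two models is not stated; section 9, part j, allows mixed designs for other measures without saying which.

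**2. Effect scale.** The protocol (section 9, part j) gives healthy-subject d = 0.91 for PPI, and from other laboratories 0.87 for MMN and 0.69 for GBS; the last is a ketamine figure. Take the standardised active-minus-placebo difference as dz = d/√2, i.e. 0.643, 0.615 and 0.488. Two-sided paired t-test at 0.05, noncentrality dz·√n:

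| Measure | n | Computed power | Protocol |
|---|---|---|---|
| PPI | 30 | 0.926 | 0.92 |
| PPI | 24 | 0.855 | 0.85 |
| MMN | 30 | 0.903 | 0.90 |
| GBS | 30 | 0.733 | 0.75 |

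The protocol does not state its formula. An independent-groups t-test gives 0.934, 0.870, 0.912 and 0.748, also within 2 points. The d/√2 scale is the cautious one: reading 0.91 as the difference-score effect itself would raise the results below.

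**3. Same-dose interaction with an HS post-hoc.** Assumptions: zero SZ effect; 30 HS and 30 SZ, all at 20 mg (Aims 2 and 3); one contrast per subject, averaged over intervals for PPI; two-sided 0.05. The interaction has 58 df, critical t = 2.002 and noncentrality dz·√(30/2). For PPI that is 0.643 × 3.873 = 2.49. The last column, from simulation, is the probability that the interaction is significant, the HS paired post-hoc is significant for active > placebo, and the SZ contrast is not significant.

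| HS effect | Measure | Noncentrality | Interaction alone | With HS post-hoc, no SZ effect found |
|---|---|---|---|---|
| Full | PPI | 2.49 | 0.688 | 0.676 |
| Full | MMN | 2.38 | 0.649 | 0.635 |
| Full | ASSR | 1.89 | 0.460 | 0.430 |
| Half | PPI | 1.25 | 0.232 | 0.186 |
| Half | MMN | 1.19 | 0.216 | 0.170 |
| Half | ASSR | 0.94 | 0.153 | 0.107 |

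**4. Pooled HS + SZ main effect.** With equal groups and no SZ effect the noncentrality is the same as in step 3. An active > placebo main effect is therefore found with probability about 0.69/0.65/0.46 at the full HS effect and 0.23/0.22/0.15 at half.

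**5. Post-hoc must be in SZ.** Same full HS effect, 30 HS and 30 + 30 SZ. The overall test is a main effect in SZ, or drug × diagnosis (HS against all SZ, 88 df), followed by a paired active > placebo test. False confirmation is 0.036/0.034/0.026 if either SZ dose group qualifies and 0.018/0.017/0.013 if only the 20 mg group does. A direct active > placebo contrast in one SZ dose group gives 0.025, whatever happens in HS.

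**The case against.** The best defence is that the SAP states its hypothesis for SZ patients, so an informative post-hoc is naturally one that informs about SZ patients. On that reading step 5 applies and the proposed fix hardly changes the error rate. The protocol already gives a patient-only, per-dose rule for PPI and a direction for the other two measures. If the named PPI model governs, no diagnosis interaction can confirm PPI at all. The reported conclusion names 20 mg in SZ, which is what an SZ contrast would produce.

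Most of this stands as to size. It does not remove the gap in the text: the SAP does not say where the post-hoc must lie, attaches no population to the main effect, and lists interactions that its own PPI model cannot test.

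A reader might infer two stronger things. One is that the confirmed results rest on healthy-subject data; nothing in either document shows this. The other is a false-confirmation rate near 80%. Figures of about 82/78/56% do arise if 20 mg HS are set against 10 and 20 mg SZ pooled, at the full HS effect with unadjusted post-hocs. That comparison mixes doses, contrary to the protocol's separate analysis of dose groups, and takes the extreme case on every input.

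**Conclusion.** The rule is wider than the hypothesis and does not fit the model named for PPI; for MMN and ASSR the model is incompletely stated. That holds on the text and needs no figure.

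The practical size turns on one undefined clause and on the unstated population of the main effect. On the natural SZ reading it is small: at most about 4% false confirmation in the scenarios run. If an HS post-hoc is allowed, it is about 68/63/43% at the full HS effect and 19/17/11% at half.

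The latter figures illustrate what the wording permits; they do not estimate what happened. They assume exactly zero SZ effect, the d/√2 scale, unadjusted post-hocs and group sizes from a protocol dated October 2010. The SAP gives no sizes and cites a grant that is not among those in protocol section 23, so the groups actually analysed may differ.

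**What to change.** - For each measure, define confirmation as a significant active > placebo effect within SZ, separately by dose group. For PPI: a drug main effect, or drug × interval with a significant active > placebo post-hoc in SZ, as in protocol section 9, part j. For MMN and ASSR: the paired active-minus-placebo contrast in SZ, in the direction the protocol gives.
- Make drug × diagnosis secondary and restrict it to groups given the same dose. Make drug × dose secondary too, with dose as a between-subject factor. State the full model for each.
- State that no interaction, and no main effect pooled over HS and SZ, confirms the SZ hypothesis by itself.
- Because results are already reported, name the model and the SZ contrast behind each confirmed statement, and label any re-run as post hoc.

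The cost is a few sentences of SAP text and at most a re-analysis of existing data; no new patients are needed. The price is that the SZ claim can no longer draw support from healthy-subject data. A rule tightened now also cannot restore prespecification; it can only make the basis of the claims visible.
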